### **12.2.3 Proportion of patients alive at 24 months (OS24)**

The proportion of patients alive at 24 months (ie, OS24) will be summarised (using the Kaplan-Meier curve) and presented by treatment arm. It will be compared between treatments by using the Kaplan-Meier estimator of survival at 24 months for each treatment to obtain the HR. The HR and CI will be presented.

### **12.2.4 Objective response rate**

The ORR will be based on the programmatically derived RECIST using the BICR data. The ORR will be compared between MEDI4736 versus placebo using a Fisher's exact test. A binary response variable for ORR will be used for the analysis with the categories of CR and PR versus SD, PD and NE. The results of the analysis will be presented in terms of the proportion of responders and a p-value.

This analysis of ORR will be repeated using the results of the programmatically derived PFS using the site Investigator data from all scans based upon RECIST as a sensitivity analysis to confirm the results of the primary analysis derived from the CRFs. An additional sensitivity analysis will be performed on ORR using BICR tumour data based upon RECIST modified for confirmation of progression to determine if there is any difference when using progression confirmation rules. Finally, an exploratory analysis of ORR using the irRC data obtained from the BICR will be performed where the above analysis will be repeated.

Summaries will be produced that present the number and percentage of patients with a tumour response (CR/PR). Overall visit response data will be listed and summarised over time for all patients (ie, the FAS). For each treatment arm, best objective response (BoR) will be summarised by n (%) for each category (CR, PR, NED, SD, PD, NE). No formal statistical analyses are planned for BoR.

### **12.2.5 Duration of response**

In order to analyse the DoR between arms the Expected Duration of Response (EDoR) will be derived for each treatment arm (Ellis et al 2008) for the BICR tumour data. The EDoR is the product of the proportion of patients responding to treatment and the mean DoR in responding patients and provides an estimate based on all randomised patients. Treatments will be compared by calculating the ratio of EDoRs, using an appropriate probability distribution (to be specified in the SAP) for DoR in responding patients. Additionally, descriptive data will be provided for the DoR in responding patients, including the associated Kaplan-Meier curves (without any formal comparison of treatment arms or p-value attached).

### **12.2.6 Proportion of patients alive and progression free at 12 months (APF12)**

The proportion of patients alive and progression free at 12 months will be summarised (using the Kaplan-Meier curve) and presented by treatment arm. Each will be compared between treatments by using the Kaplan-Meier estimator of PFS at 12 months for each treatment to obtain the HR. The HR and CI will be presented.

### **12.2.7 Proportion of patients alive and progression free at 18 months (APF18)**

The proportion of patients alive and progression free at 18 months will be summarised (using the Kaplan-Meier curve) and presented by treatment arm. Each will be compared between treatments by using the Kaplan-Meier estimator of PFS at 18 months for each treatment to obtain the HR. The HR and CI will be presented.

### **12.2.8 Time from randomisation to second progression (PFS2)**

PFS2 will be analysed using identical methods as outlined for the analysis of PFS and adjusting for the same set of covariates, but no subgroup analysis will be performed. Medians and Kaplan-Meier plots will be presented to support the analysis. The sensitivity analysis outlined in Section 12.2.2.2 will not be repeated for PFS2 with the exception of a Kaplan-Meier plot of the time to censoring where the censoring indicator of PFS2 is reversed.

### **12.2.9 Time to death or distant metastasis**

TTDM will be analysed using identical methods as outlined for the analysis of PFS and adjusting for the same set of covariates, but no subgroup analysis will be performed. Medians and Kaplan-Meier plots will be presented to support the analysis. The sensitivity analysis outlined in Section 12.2.2.2 will not be repeated for TTDM with the exception of a Kaplan-Meier plot of the time to censoring where the censoring indicator of TTDM is reversed.

### **12.2.10 Patient reported outcomes**

The PRO endpoints that have been identified as primary are EORTC QLQ-C30 time to QoL deterioration of global health status and LC13 time to symptom deterioration for each of dyspnoea, cough, haemoptysis, and pain. These are not part of the main multiple testing procedure but as supportive endpoints will need a Bonferroni adjustment to the significance level to aid interpretation. Therefore, these 5 endpoints will be tested at a 1% significance level and 99% CIs will be produced.

The other time to symptom deterioration endpoints will be tested at a 5% significance level and 95% CIs will be produced.

#### **12.2.10.1 EORTC QLQ-C30**

Time to symptom deterioration will be analysed for each of the 3 symptom scales (fatigue, pain, nausea/vomiting) and the 5 individual symptom items (dyspnoea, insomnia, appetite loss, constipation, diarrhoea). Time to QoL/function deterioration will be analysed for the 5 function scales (physical, role, emotional, cognitive, and social) and global health status/QoL. This will be achieved by comparing between treatment arms using a stratified log-rank test as described for the primary analysis of OS. The sensitivity analysis to ascertain attrition bias will be performed as described for the primary analysis of OS for those endpoints identified as primary. However, subgroup analyses and treatment interaction testing will not be performed. The HR and 95% CI for each scale/item will be presented graphically on a forest plot.

A summary of the symptom improvement rate for each of the 3 symptom scales and the 5 individual symptom items will be produced. Similarly, a summary of QoL/function improvement rate for each of the 5 function scales (physical, role, emotional, cognitive, and social) and global health status/QoL will be produced. Symptom improvement rate and QoL/function improvement rate will be analysed by comparing between treatment arms using a logistic regression model. The odds ratio and 95% CI for each scale/item will be presented graphically on a forest plot. If there are very few responses in one treatment arm, a Fisher's exact test will be considered.

For each of the 3 symptom scales (fatigue, pain, nausea/vomiting), 5 individual symptom items (dyspnoea, insomnia, appetite loss, constipation, diarrhoea), 5 functional scales (physical, role, emotional, cognitive, and social), and global health status/QoL, time to deterioration will be presented using a Kaplan-Meier plot. Summaries of the number and percentage of patients experiencing a clinically meaningful deterioration or death, and the median time to deterioration will also be provided for each treatment arm.

Summaries of original and change from baseline values of each symptom scale/item, the global HRQoL score and each functional domain will be reported by visit for each treatment arm. Graphical presentations may also be produced as appropriate. Summaries of the number and percentage of patients in each response category at each visit for each ordinal item (in terms of the proportion of patients in the categories of improvement, no change, and deterioration as defined in Section 11.3.1.1) will also be produced for each treatment arm.

#### 12.2.10.2 LC13

Time to symptom deterioration for each of the 6 individual symptoms (dyspnoea, cough, haemoptysis, chest pain, arm/shoulder pain, other pain) will be compared between treatment arms using a stratified log-rank test as described for the primary analysis of OS. The sensitivity analysis to ascertain attrition bias will be performed as described for the primary analysis of OS for those endpoints identified as primary. However, subgroup analyses and treatment interaction testing will not be performed. The HR and 95% CI for each scale/item will be presented graphically on a forest plot.

For each of the 6 symptoms items in LC13, time to deterioration in symptoms will be presented using a Kaplan-Meier plot. Summaries of the number and percentage of patients experiencing a clinically meaningful deterioration or death, and the median time to deterioration will also be provided for each treatment arm.

A summary of the symptom improvement rate for each of the 6 individual symptom items will be produced. The symptom improvement rate will be compared between treatment arms using a logistic regression model. The odds ratio and 95% CI for each symptom will be presented graphically on a forest plot. If there are very few responses in one treatment arm, a Fisher's exact test will be considered.

Summaries of original and change from baseline values of each symptom (dyspnoea, cough, haemoptysis, chest pain, arm/shoulder pain, other pain) and each treatment-related side effect

(sore mouth, dysphagia, peripheral neuropathy and alopecia) will be reported by visit for each treatment arm. Graphical presentations may also be produced as appropriate. Summaries of the number and percentage of patients in each response category at each visit for each ordinal symptom item (in terms of the proportion of patients in the categories of improvement, no change, and deterioration as defined in Section 11.3.1.2) will also be produced for each treatment arm.

#### 12.2.10.3 EuroQol-5-Dimension 5-Level questionnaire

The change from baseline in health state utility values and the visual analogue scale will be compared between treatment arms at each visit using a mixed model repeated measures analysis, which adjusts for the same factors as the primary analysis and also the baseline health state utility value/visual analogue scale as appropriate. Adjusted mean differences between treatments and 95% CIs from these analyses will be presented, but, as this analysis is exploratory in nature, p-values will not be calculated.

Descriptive statistics will be reported for the health state domain (eg, proportion in each domain) and the visual analogue scale by visit, as well as the change in the visual analogue scale value and the derived utility index value from baseline. To support future economic evaluations, additional appropriate analyses may be undertaken, for example, mean health state utility pre- and post-treatment, and pre- and post-progression.

#### 12.2.11 Healthcare resource use

An exploratory health economic analysis of hospital episodes including type of contact (hospitalisation, outpatient, day case), reason, length of stay by ward type (including intensive care unit) and procedures and tests may be undertaken to examine the impact of disease and treatment on resource use to primarily support the economic evaluation of MEDI4736. This would include providing descriptive statistics as appropriate, including means, median and ranges.

#### 12.2.12 Safety data

Safety and tolerability data will be presented by treatment arm using the safety population.

Data from all cycles of treatment will be combined in the presentation of safety data. AEs (both in terms of MedDRA preferred terms and CTCAE grade) will be listed individually by patient. The number of patients experiencing each AE will be summarised by treatment arm and CTCAE grade. Additionally, data presentations of the rate of AEs per person-years at risk may be produced. Any safety summaries examining re-treatment with MEDI4736 will be produced separately.

Other safety data will be assessed in terms of physical examination, clinical chemistry, haematology, vital signs and ECGs. Exposure to MEDI4736 and placebo will be summarised. Time on study and MEDI4736/placebo dose interruptions will also be summarised. At the end of the study, appropriate summaries of all safety data will be produced, as defined in the SAP.

### **12.2.13 PK data**

MEDI4736 concentration data will be listed for each patient and each dosing day, and a summary provided for all evaluable patients.

#### **12.2.13.1 Immunogenicity analysis**

Immunogenicity results will be listed by patient and a summary will be provided of the number and percentage of patients who develop detectable anti-MEDI4736 antibodies. The immunogenicity titre and neutralising ADA data will be listed for samples confirmed positive for the presence of anti-MEDI4736 antibodies.

### **12.2.14 PK/PDx relationships**

If the data are suitable, the relationship between MEDI4736 PK exposure and efficacy/safety parameters may be investigated graphically or using appropriate data modelling approach.

### **12.2.15 Biomarker data**

The relationship of PD-L1 expression and if applicable, of exploratory biomarkers to OS, PFS, ORR and DoR will be presented for a subset of patients in the ITT population who are evaluable for each biomarker.

This will be assessed using similar summary and graphical representations to those that are outlined for the efficacy outputs in Section [12.2.2](#) to [12.2.5](#).

PD-L1 expression determined by immunohistochemistry will be reported in the CSR. Summaries and analyses for exploratory biomarkers will be documented in a separate analysis plan and will be reported outside the CSR in a separate report.

### **12.2.16 Interim analysis**

Up to 3 interim analyses will be performed, one for PFS and two for OS. The DCO for the interim analysis of PFS will occur when it is expected that 367 PFS events have occurred (52% maturity, approximately 30 months after the first patient is randomised). The DCO for the first interim analysis of OS will occur when it is expected that 458 PFS events have occurred (65% maturity, approximately 36 months after the first patient is randomised). It is expected that approximately 285 death events (41% maturity) will be available for the interim OS analysis (assuming OS HR=0.73). The second interim analysis of OS (the third interim analysis) will be conducted when it is expected that 393 OS events have occurred (56% maturity, approximately 47 months after the first patient is randomised). The interim analyses will be assessed by an IDMC (further details are given in the IDMC charter). It is expected that recruitment will have completed prior to the results of these interim analyses being available.

#### 12.2.16.1 PFS interim analysis

Approximately 367 PFS events (52% maturity) will be available for the interim PFS analysis.

The Lan DeMets spending function that approximates an O'Brien Fleming approach will be used to account for multiplicity introduced by including an interim analysis for superiority (Lan and DeMets 1983).

The criterion for superiority is a statistically significant improvement in PFS at the interim analysis. If 80% of the PFS events required at the time of the primary PFS analysis is available at the time of the interim (ie, 367/458 PFS events have occurred), the 2-sided significance level to be applied for the PFS interim analysis would be 1.04% and the 2-sided significance level to be applied for the primary PFS analysis would be 2.19%.

If the PFS results indicate superiority, then analyses of all other endpoints may also be performed. Patients would continue to be followed for PFS and survival until approximately 458 PFS events, when the primary PFS analysis and the first interim OS analysis would be performed.

If the PFS interim analysis result does not meet the criterion of stopping for superiority, then all patients will remain blinded and continue to be followed for PFS and OS.

The recommendations from the IDMC will not reveal the results of the analysis but will take the form of "Continue/Modify/Stop".

#### 12.2.16.2 OS interim analyses

Approximately 285 and 393 death events (41% and 56% maturity) will be available for the first and the second interim OS analysis, respectively (assuming OS HR=0.73).

The Lan DeMets spending function that approximates an O'Brien Fleming approach will be used to account for multiplicity introduced by including an interim analysis for superiority (Lan and DeMets 1983).

The criterion for superiority is a statistically significant improvement in OS at the interim analyses. If 58% or 80% of OS events required at the time of the primary OS analysis is available at the time of the interim (ie, 285/491 or 393/491 events have occurred), the 2-sided significance level to be applied for the OS interim analysis would be 0.21% and 0.98%, respectively, and the 2-sided significance level to be applied for the primary OS analysis would be 2.17%.

If the PFS and/or OS results indicate superiority, then analyses of all other endpoints would be performed and the results of these analyses will form the basis for submissions for regulatory approval. Patients would continue to be followed for survival until approximately 491 patients have died, when an updated analysis would be performed.

If the PFS result is not statistically significant and/or either of the OS interim analysis result does not meet the criterion of stopping for superiority, then all patients will remain blinded and continue to be followed for survival.

The recommendations from the IDMC will not reveal the results of the analysis but will take the form of “Continue/Modify/Recommend Early Submission/Stop”.

### **12.3 Determination of sample size**

The sample size for this study was selected to be consistent with the research hypothesis as described in Section 1.2.

The two co-primary endpoints of this study are OS and PFS. To control for type-I error, a significance level of 2.5% will be used for analysis of OS and a significance level of 2.5% will be used for analysis of PFS. The study will be considered positive (a success) if either the PFS analysis results and/or the OS analysis results are statistically significant.

Approximately 702 patients will be randomised 2:1 to obtain 491 death events in the ITT population (70% maturity). The primary PFS analysis DCO will occur when it is expected that 458 PFS events have occurred (65% maturity). If the true PFS HR is 0.67, the study will provide at least 95% power to demonstrate a statistically significant difference for PFS with a 2-sided significance level of 2.5% in the ITT population; this translates to a 5-month benefit in median PFS over 10 months on placebo if PFS is exponentially distributed. The smallest treatment difference that would be statistically significant is a HR of 0.8. A recruitment period of approximately 22 months and a follow-up period of 14 months are expected for the PFS endpoint. Therefore it is anticipated that this PFS analysis could be performed approximately 36 months after the first patient has been randomised.

The primary OS analysis DCO will occur when it is expected that 491 OS events have occurred (70% maturity). If the true OS HR is 0.73, this number of death events will provide at least 85% power to demonstrate a statistically significant difference for OS, assuming a 2.5% 2-sided significance level in the ITT population; this translates to an 8-month benefit in median OS over 22 months on placebo if OS is exponentially distributed. The smallest treatment difference that would be statistically significant is a HR of 0.81. A recruitment period of approximately 22 months and a follow-up period of 40 months are expected for the OS endpoint. Therefore it is anticipated that this OS analysis could be performed at approximately 62 months after the first patient has been randomised.

Please refer to [Appendix D](#) for information on PGx.

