The first interim OS analysis for superiority will occur at the time of the primary PFS analysis and the second interim OS analysis will occur when it is expected that 393 OS events have occurred. The 2.5% alpha level allocated to OS will be controlled at the interim and primary time point by using the Lan DeMets ([Lan and DeMets 1983](#)) spending function that approximates an O'Brien Fleming approach, where the significance level applied at the interim depends upon the proportion of information available. For example, if 58% and 80% of OS events required at the time of the primary OS analysis is available at the time of the interim (ie, 285/491 and 393/491 events have occurred), the 2-sided significance level to be applied for the OS interim analysis would be 0.21% and 0.98% respectively, and the 2-sided significance level to be applied for the primary OS analysis would be 2.17%.

At the time of the primary PFS, interim OS and primary OS analyses, hypotheses will be tested using a multiple testing procedure with an alpha-exhaustive recycling strategy ([Burman et al 2009](#)). With this approach, hypotheses will be tested in a pre-defined order. At the time of the primary PFS analysis, the PFS endpoint will be tested first and at the time of the primary OS analysis, the OS endpoint will be tested first. The other hypotheses will then be tested in the multiple testing procedure using a weighted proportion of alpha (test mass; the total test mass equals alpha) and test mass that becomes available after each rejected hypothesis is recycled to the hypotheses not yet rejected. This testing procedure stops when the entire test mass is allocated to non-rejected hypotheses. Implementation of this pre-defined ordered testing procedure, including recycling, will strongly control type I error at 5% (2-sided), amongst all key hypotheses.

At the primary PFS analysis, if significance is achieved on the primary PFS analysis, then the alpha will be recycled to OS primary analysis followed by the secondary endpoints, OS24 and ORR.

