An interim OS analysis for superiority will occur at the time of the primary PFS analysis. The 2.5% alpha level allocated to OS will be controlled at the 2 interim and primary time point by using the Lan DeMets ([Lan and DeMets 1983](#)) spending function that approximates an O'Brien Fleming approach, where the significance level applied at the interim depends upon the proportion of information available. For example, if 58% or 80% of OS events required at the time of the primary OS analysis is available at the time of the interim (i.e., 285/491 or 393/491 events have occurred), the 2-sided significance level to be applied for the OS interim analysis would be 0.21% and 0.98% and the 2-sided significance level to be applied for the primary OS analysis would be 2.17%.

The family wise error rate (FWER) will be strongly controlled for the testing of PFS, OS, OS24, and ORR including interim analyses by applying the testing procedure illustrated in the Figure 2 below.

The PFS and OS will be tested according to the group sequential Holm fixed (GSHf) procedure described in [Ye et al 2012](#). In this procedure, the testing will start from PFS, if the testing for PFS is significant at the alpha level specified in Figure 2 at either interim or primary analysis the full 2.5% alpha level for PFS can be propagated to the testing of OS, which means that the OS will be tested at an overall alpha level of 5%. Following the GSHf procedure the alpha level for the interim analyses of OS will not be changed but the alpha level for the primary analysis of OS will be recalculated based on 5% alpha level overall with interim alpha levels as specified in Figure 2. For example, if the information fraction for the interim analyses is as specified (80% for PFS interim and 58%/80% for OS interims) the alpha level for the primary OS analysis will be 4.85% so that the FWER for OS is 5% accounting

[figure not shown]
for interim analyses, given testing of PFS is significant at interim ($\alpha=1.04\%$) or at primary analysis ($\alpha=2.19\%$). The alpha level for the interim OS analyses will remain at 0.21% and 0.98%.

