If the testing for PFS is not significant at either the interim ($\alpha=1.04\%$) or at the primary analysis ($\alpha=2.19\%$), the OS will be tested at the levels specified in [Figure 2](#). In this case if the testing for OS is significant at any interim analysis or primary analysis the full 2.5% alpha level for OS can be propagated to the testing of PFS, which means that the PFS will be tested at an overall alpha level of 5%. Following GSHf, the alpha level for the interim analysis of PFS will not be changed but the alpha level for the primary analysis of PFS will be recalculated based on 5% alpha level overall with interim alpha levels as specified in [Figure 2](#). For example, if the information fraction for the interim analyses is as specified (80% for PFS interim and 58%/80% for OS interim) the alpha level for the primary PFS analysis will be 4.88%, given testing of OS is significant at interim ($\alpha=0.21\%$ and 0.98%) or at primary analysis ($\alpha=2.17\%$). The alpha level for the interim PFS analysis will remain at 1.04%.

OS24 and ORR will not be tested unless the null hypotheses for both PFS and OS are rejected according to the GSHf procedure described above. After both PFS and OS are rejected the OS24 will be tested with 5% alpha level controlled at the interim and primary time point. The interim analyses of OS24 will use the same interim alpha level for OS at the same analysis point. The alpha for primary analysis of OS24 will be calculated based on interim alpha levels and information fractions at the interim so that the alpha level for OS24 is controlled at 5% overall. ORR will only be tested after the null hypothesis of PFS, OS, and OS24 are all rejected and ORR will be tested at a 5% level.

The FWER is strongly controlled at 5% for PFS and OS according to [Ye et al 2012](#). The FWER for PFS, OS, and OS24 is also strongly controlled at 5% due to the fix-sequence testing nature and according to [Glimm et al 2009](#). Finally the FWER is still strongly controlled after adding the fix-sequence testing of ORR. So the FWER is strongly controlled at 5% for the testing of all four endpoints. [Figure 2](#) shows the multiple testing framework.

Figure 2 Multiple testing procedures for controlling the type 1 error rate

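### Is the smallest significant OS hazard ratio of 0.81 wrong because the final OS test may be run at 4.85% rather than 2.5%?

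*Protocol*

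**What the plan says.** Protocol 12.3 allocates 2.5% to OS and 2.5% to PFS. It then sizes OS in one run of sentences: "If the true OS HR is 0.73, this number of death events will provide at least 85% power", with the level stated as "assuming a 2.5% 2-sided significance level in the ITT population". The critical value follows directly: "The smallest treatment difference that would be statistically significant is a HR of 0.81". The synopsis and SAP 1.3 give the same figures in the same order. For PFS the matching statement is a hazard ratio of 0.8 at 458 events, also at 2.5%.

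The levels for the actual analyses are set elsewhere. Protocol 12.2.16.2, at the planned information fractions and without recycling, says "the 2-sided significance level to be applied for the primary OS analysis would be 2.17" per cent. Protocol 12.2.1 adds that if PFS is significant "then the alpha will be recycled to OS primary analysis". SAP 4.1.2 turns this into a figure: "the alpha level for the primary OS analysis will be 4.85" per cent. In the reverse case, where PFS has missed its own level and OS succeeds, "the alpha level for the primary PFS analysis will be 4.88" per cent. The OS interim levels stay at 0.21% and 0.98% on either route.

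**The concern.** A critical hazard ratio depends on the level at which the test is run, and no single OS look is run at exactly 2.5%. The final level is 2.17% without recycling and 4.85% with it. PFS success is the expected route, since PFS power is about 96% at 2.19% if the true hazard ratio is 0.67. Someone reading Protocol 12.3 alone might therefore conclude that an observed OS hazard ratio of 0.82 at 491 deaths would fail, when under SAP 4.1.2 it would be significant after a PFS success. Had the stated figure been a decision boundary, or had it been miscalculated, the final OS result could be misread.

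**Working it through.** **Inputs.** 491 deaths, 458 PFS events, 2:1 allocation, OS hazard ratio 0.73 and PFS hazard ratio 0.67 (Protocol 12.3). Final levels 2.17% and 2.19% (Protocol 12.2.1 and 12.2.16) and 4.85% and 4.88% (SAP 4.1.2).

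**Formula.** Critical HR = exp(−z/√V), where V = events × (2/3) × (1/3) and z is the two-sided normal quantile.

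**The plan's own figure.** V = 491 × 2/9 = 109.1 and √V = 10.446. At 2.5%, z = 2.2414, so exp(−2.2414/10.446) = 0.807. This is the stated 0.81. Power on the same basis: −ln(0.73) × 10.446 = 3.287, and Φ(3.287 − 2.2414) = 85.2%, matching the stated minimum of 85%.

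**The levels behind the other routes.** Multivariate normal integration at 285, 393 and 491 deaths, with interim levels 0.21% and 0.98%, gives a final level of 2.17% for 2.5% overall and 4.86% for 5% overall (SAP: 4.85%). The PFS counterparts come out at 2.19% and 4.88%.

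**Critical hazard ratios by level.**

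| Endpoint | Level | z | Critical HR |
|---|---|---|---|
| OS, 491 deaths | 2.5% | 2.2414 | 0.807 (stated 0.81) |
| OS | 2.17% | 2.2956 | 0.803 |
| OS | 4.85% | 1.9730 | 0.828 |
| PFS, 458 events | 2.5% | 2.2414 | 0.801 (stated 0.8) |
| PFS | 2.19% | 2.2921 | 0.797 |
| PFS | 4.88% | 1.9703 | 0.823 |

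**Sensitivity to the variance.** A log-rank variance simulated under assumptions (exponential times, uniform 22-month accrual, no dropout, no stratification, true OS HR 0.73 to 0.83) gives V of 102.4 to 105.3. The critical OS values are then 0.801 to 0.804 at 2.5%, 0.797 to 0.800 at 2.17% and 0.823 to 0.825 at 4.85%. The choice of variance alone moves the 2.5% value between 0.801 and 0.807. That is wider than the gap of 0.807 − 0.803 = 0.004 between the 2.5% and 2.17% values.

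**The example of 0.82.** −ln(0.82) × 10.446 = 2.073, so p = 0.038 (0.045 with V = 102.5). At 2.5%, the level the sentence names, this is not significant, as the text implies. At 4.85% it is significant, and the sentence does not address that case.

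**The case for a change.** The strongest case against the wording is that stating a condition explains the number without making it the trial's threshold. The sentence speaks of what would be significant. That depends on the level applied, and the level at the primary OS analysis is 2.17% or 4.85%. On the likelier route the threshold is 0.82 to 0.83, and Protocol 12.3 neither says so nor points to the recycling.

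Part of this stands. The final look is not itself run at 2.5%, the arithmetic for 4.85% is right, and a cross-reference would help a reader who opens only that section. It does not amount to an error, for three reasons. First, 2.5% is the total alpha first allocated to OS across its three looks, and Protocol 12.2.2.1 reports OS with a 97.5% confidence interval, so it is a level the plan really uses. Second, 2.17% and 4.85% are given as examples at 58% and 80% information and will move with the actual event counts; critical values built on them would be just as conditional. Third, the power of at least 85% rests on the same 2.5%. It becomes 83.9% for the final look alone at 2.17% and 90.6% at 4.85%. If that convention is acceptable for power, it is acceptable for the hazard ratio quoted beside it.

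**Conclusion.** The concern does not hold. The figure 0.81 is correct at the level stated next to it, and the same is true of 0.8 for PFS. Relative to the recycled level the sizing text is conservative by about 0.02 on the hazard-ratio scale (0.807 against 0.828, or 0.823 to 0.825 with the simulated variance). Relative to 2.17% it is looser by 0.004, less than the uncertainty from the variance method. The testing rules in Protocol 12.2.1 and SAP 4.1.2 disclose the other levels, and those levels reproduce. Success is judged on the stratified log-rank p-value, so no patient number, event number, alpha level or conclusion turns on this sentence. The synopsis also records that the planned analyses had concluded by Amendment 07. Listing the critical value for each route would be a matter of preference. These figures assume 491 deaths and 458 PFS events, 2:1 allocation, proportional hazards and the planned information fractions.
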